8.3 Phase 1b Modakafusp Alfa SA Dose Escalation Schema

The 2-parameter BLRM implementing the EWOC principle will be used to inform dose escalation decisions and MTD estimation starting from the second dose cohort. The final decision on next dose level will be taken jointly by the sponsor and the participating investigators.

BLRM with overdose control ([Appendix E](#)) will be used to inform dose escalation decisions and MTD estimation, along with consideration of other emerging safety, clinical, PK, and pharmacodynamic data. Doses will be escalated as shown in [Table 8.a](#).

Table 8.a **Planned Dose Levels**

Dose Level	Dose (Unit)
-1	0.05 mg/kg
1	0.1 mg/kg
2	0.2 mg/kg
3	0.4 mg/kg
4	0.75 mg/kg
5	1.5 mg/kg
6	3.0 mg/kg
7	6.0 mg/kg

More conservative dose escalation, evaluation of intermediate doses, and expansion of an existing dose level are all permissible following discussions between the sponsor and the investigators, if such measures are needed for patient safety or for a better understanding of the dose-related toxicity, exposure, or pharmacodynamics. The initial size of each cohort will be approximately 3 evaluable patients.

Initially, 3 patients will be enrolled at the 0.1 mg/kg starting dose level. The following rules will be used only for this initial cohort:

- If none of the 3 patients experiences a DLT during the first cycle, the dose may be escalated to the next planned dose level.
- If 1 of the 3 patients exhibits a DLT, then the cohort will be expanded from 3 patients to a total of 6 patients.
 - If no more than 1 patient out of the 6 total patients has a Cycle 1 DLT, 3 patients will be enrolled at the next dose level.
 - If 2 of the 6 patients have a Cycle 1 DLT, 3 additional patients will be enrolled. If any of the 3 additional patients have a Cycle 1 DLT, the starting dose will be considered not tolerated and the dose will be de-escalated to 0.05 mg/kg. If none of the 3 additional patients have a Cycle 1 DLT, the starting dose may be considered the MTD or may be escalated to the next dose level, after consideration of other available safety, clinical, PK, and pharmacodynamic data.
 - If 3 or more of the 6 patients experience a Cycle 1 DLT, the starting dose level will be considered not tolerated and the dose will be de-escalated 0.05 mg/kg following review of all available safety data and approval of the sponsor.

- If 2 or more of the 3 patients experience a DLT, then the starting dose level will be considered too toxic and the dose will be de-escalated to 0.05 mg/kg.

Starting from the second dose level, the BLRM with overdose control will be used for all subsequent dose escalation recommendations. The BLRM recommended dose at the end of each dosing cohort will be that which has the highest posterior probability of having a DLT rate that is ≥ 0.16 and ≤ 0.33 . Following the EWOC principle, the posterior probability of the recommended dose having a DLT rate above 0.33 must not exceed 35%. Escalation will continue until one of the following stopping rules is met before reaching the maximum number of patients:

- At least 6 patients are enrolled at the current dose, the current dose is the BLRM recommended dose for the next group of patients, and the observed DLT rate is $\leq 33\%$, OR
- At least 9 patients are enrolled at the next recommended dose, the BLRM posterior probability of the next recommended dose having a DLT rate that falls into the interval (0.16, 0.33) exceeds 50%, and the observed DLT rate is $\leq 33\%$.

Once either of the above rules has been met, the MTD may be declared. Alternative stopping rules may also be considered following discussions between the sponsor and the investigators.

The description and operating characteristics of the BLRM for dose escalation are included in [Appendix E](#).

8.4 Phase 2 Modakafusp Alfa Dose Expansion

A minimum of 3 patients will be enrolled at the modakafusp alfa RP2D in combination with pembrolizumab 400 mg Q6W to evaluate safety and tolerability in a single safety lead-in phase. The safety lead-in phase will start with the enrollment of 3 initial patients to evaluate the tolerability during the Cycle 1 DLT evaluation period of modakafusp alfa with pembrolizumab. If there are no DLTs in the first 3 patients during Cycle 1 of the safety lead-in period with modakafusp alfa SA RP2D in combination with pembrolizumab 400 mg Q6W, the combination dose and regimen could be selected for the 3 melanoma disease cohorts.

If there is 1 DLT in the initial 3 patients in the safety-lead in period, an additional 3 patients will be enrolled at the same modakafusp alfa RP2D in combination with pembrolizumab 400 mg Q6W. If there are ≥ 2 DLTs in the first 3 patients at the modakafusp alfa SA RP2D, enrollment will resume at the next lower dose level of modakafusp alfa RP2D in combination with pembrolizumab. Other approved pembrolizumab dosing regimens (ie, 200 mg Q3W) could be tested in the safety-lead in period if 400 mg Q6W in combination with modakafusp alfa at one dose lower than RP2D is intolerable. For the safety lead-in period, patient enrollment will be staggered between the first and second patients by 7 days in the first dose cohort. The second and third patients can be dosed concurrently if the first patient in the cohort has gone through the Day 8 visit without clinically significant acute toxicities. Subsequent cohorts, if any, will not require staggering between patients.

8.5 Additional Safety Stopping Rules

Patients will be monitored continuously for safety. Circumstances that may warrant enrollment hold include the following:

- Fatal Events:
 - A threshold for related fatal AEs of 6% is proposed for the whole trial (dose escalation plus expansions). If this mark is passed during the expansion phase, enrollment will be halted, and the safety of the dose selected will be re-evaluated.
 - During dose escalation, enrollment will be stopped if ≥ 2 related Grade 5 AEs happen in the first 12 (16%) patients or if ≥ 3 (10%) events happen in 30 patients. If escalation goes beyond 30 patients, the 6% mortality threshold will be used.
- Nonfatal Events:
 - In escalation phase, dose escalation rules based on DLTs and guided by BLRM will be implemented.
 - Additionally, Grade 4 life-threatening, related, nonhematologic AEs must stay $< 10\%$ during the trial once 30 patients have been dosed.

In these circumstances, the final decision about trial execution will be made after a full review of the safety data by the sponsor and the Safety Management Team.

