6.2 Number of Patients

It is expected that approximately 30 patients will be enrolled in the phase 1b dose escalation phase at approximately 3 to 4 sites. Up to 25 patients will be enrolled in each of the 3 combination therapy cohorts. A Bayesian predictive probability design was used to allow multiple interim analyses for early termination due to futility. Assuming 3 to 9 safety lead-in patients, the total sample size for phase 2 can be up to 84 patients.

The study is expected to enroll up to 114 patients overall.

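### Section 8.5's fatal-event rules do not join up at 30 patients, and the pooled 6% mark makes the trigger for combination deaths depend on single-agent history

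*Protocol*

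**What the plan says.** Protocol section 8.5 introduces its fatal and nonfatal rules with "Circumstances that may warrant enrollment hold include the following", and leaves the final decision to a full safety review by the sponsor and the Safety Management Team. For related deaths it gives three statements:

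- A trial-wide mark: "A threshold for related fatal AEs of 6% is proposed for the whole trial (dose escalation plus expansions". On its effect: "If this mark is passed during the expansion phase, enrollment will be halted, and the safety of the dose selected will be re-evaluated".
- An escalation rule, under which enrollment stops if two or more "related Grade 5 AEs happen in the first 12 (16%) patients or if ≥ 3 (10%) events happen in 30 patients" (three or more, in the second limb).
- A switch: "If escalation goes beyond 30 patients, the 6% mortality threshold will be used".

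On size, section 6.2 says "It is expected that approximately 30 patients will be enrolled in the phase 1b dose escalation phase" and "Assuming 3 to 9 safety lead-in patients, the total sample size for phase 2 can be up to 84 patients".

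The lead-in has a further rule. Under section 8.2 a Grade 5 event in Cycle 1 is a DLT unless clearly unrelated to modakafusp alfa. Under section 8.4, two or more DLTs in the first 3 lead-in patients move enrollment to the next lower dose level. Section 11.0 provides for no external data safety monitoring committee. The SAP does not describe the fatal-event rule, and neither document gives operating characteristics for it.

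**The concern.** Two separate features of section 8.5 need attention.

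First, the mark is declared for escalation plus expansion, but the escalation counts accept a state that already exceeds it. A trial in that state meets its escalation rule and is over the trial-wide mark at the same moment. The text does not say what follows when expansion opens, or when a 31st escalation patient is dosed.

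Second, the denominator of the 6% combines patients on modakafusp alfa alone with patients on modakafusp alfa plus pembrolizumab. The escalation patients are spread over doses from 0.1 to 6 mg/kg and receive no pembrolizumab, while section 4.3.5 warns that immune toxicities may be enhanced by the combination. They say little about mortality on the combination, yet they make up most of the denominator when the first combination patients are treated.

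At stake is whether the mortality trigger for a new combination responds to deaths on that combination or to what happened earlier in escalation.

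**Working it through.** **The plan's own figures.** 2/12 = 16.7% (printed as 16%) and 3/30 = 10.0%. 3 × 25 + 9 = 84 combination patients, and 84 + 30 = 114 in total. All reproduce.

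**Where the rules meet.** Two related deaths, at most one of them in the first 12 patients, do not stop escalation at 30. The ratio is then:

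| Patients | 30 | 31 | 32 | 33 | 34 |
|---|---|---|---|---|---|
| 2 deaths / patients | 6.67% | 6.45% | 6.25% | 6.06% | 5.88% |

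The 6% mark is exceeded from patient 30 to patient 33 with no further event. For a true related-death rate p, the chance of ending escalation in this state is [C(30,2) − C(12,2)] p²(1−p)²⁸ = (435 − 66) p²(1−p)²⁸ = 369 p²(1−p)²⁸. That is 8.4% at p = 2%, 23.5% at 6% and 19.3% at 10%. The documents give no value for p; this range is an assumption.

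**Pooled denominator.** Let N be the number of single-agent patients, s their related deaths, m the combination patients treated and k their related deaths. Reading the mark as passed when it is strictly exceeded, the rule fires if (s + k)/(N + m) > 0.06.

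With N = 30 and s = 0:

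- One combination death never fires it (at most 1/31 = 3.2%).
- Two fire it only up to m = 3 (2/33 = 6.06%). Two in 4 is 2/34 = 5.9% and does not.
- Three fire it up to m = 19 (3/49 = 6.12%). Three in 20 is 3/50 = 6.0% and does not.
- At full enrollment, 6/84 = 7.1% on the combination does not, because 6/114 = 5.3%.

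With other histories:

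- N = 24, s = 0: both small examples fire (2/28 = 7.1%, 3/44 = 6.8%).
- N = 30, s = 1: one combination death fires it up to m = 3, and two up to m = 19.
- N = 30, s = 2: the mark is already exceeded at m = 1 to 3 with no combination death.

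**Halt probabilities.** These come from an exact patient-by-patient binomial recursion. It assumes independent deaths, each counted when the patient is treated. At an assumed 10% fatal rate on the combination:

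| Single-agent history | Halt by 12 combination patients | Halt by 30 |
|---|---|---|
| 30 patients, 0 deaths | 12% | 41% |
| 24 patients, 0 deaths | 24% | 52% |
| 30 patients, 1 death | 44% | 71% |

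The true combination rate is the same in every row. Only the escalation history differs.

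**Price of separate counting, as an illustration only.** Apply section 8.5's escalation counts to the first 30 combination patients and compare with the pooled rule (N = 30, s = 0), halts by 30:

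| True combination rate | Escalation counts, combination only | Pooled 6% |
|---|---|---|
| 2% | 3.7% | 0.8% |
| 4% | 15% | 5% |
| 6% | 31% | 15% |
| 10% | 62% | 41% |

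Changing only the denominator would also be costly. A 6% mark on combination patients alone would be passed by a single death up to m = 16. At a true 2% rate it would fire in 28% of trials by m = 20, against 0.7% for the pooled rule.

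**The case against.** The strongest reply has four parts.

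- **The rules act in different periods.** The counts govern escalation up to 30 patients, and the 6% governs expansion or escalation beyond 30. A reader might infer that they contradict each other. They do not give opposite instructions for the same patients. The fault is an undefined hand-over. It is also not certain that a trial at 2/30 would be halted on its first expansion patients: the ratio is already above 6% and falling, so one can argue that nothing is newly passed in expansion. That both readings are open is the problem.
- **There are other protections.** A reader might take the 6% mark to be the only mortality trigger for the combination. It is not. Cycle 1 deaths in the lead-in count as DLTs, section 8.2 has later DLT-type events bear on the suitability of the MTD as RP2D, section 8.5's list is open-ended, and SAEs are reported within 24 hours. This stands. But the lead-in rule covers only 3 to 9 patients in Cycle 1, section 8.4 states no action for a second DLT among six, and none of these provisions sets a count for deaths after Cycle 1 or in the expansion cohorts.
- **The dilution depends on the scenario.** It is greatest with about 30 single-agent patients and no related deaths. The simulated average escalation size in protocol Appendix E is 5.9 to 24.2 patients, and at 24 the two small examples disappear. One single-agent death makes the pooled rule more sensitive at a 10% rate (44% and 71%) than the escalation counts on combination patients alone (34% and 62%). This also stands, and it supports the narrower point that escalation history drives the trigger.
- **Separate counting costs more than the 2% case suggests.** At a true 6%, which does not exceed the protocol's own mark, the illustrative counts halt 31% of trials against 15%. Those counts also end at 30, while up to 84 combination patients are planned. Both points are right, which is why no limit is proposed here.

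**Conclusion.** The concern holds in a limited form. Section 8.5 allows escalation to end at 6.7% against a whole-trial mark of 6%, leaves that mark exceeded until patient 33 with no new death, and does not say what happens then. If the true rate lies between 2% and 10%, the chance of reaching that state is about 8% to 24%.

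The pooled 6% mark is insensitive to combination deaths when escalation had about 30 patients and no related deaths, and much more sensitive after one or two. It would be too strong to call it blind: even after 30 single-agent patients without a related death, it fires at 2 deaths in the first 2 or 3 combination patients, or 3 within 19. Nor do the early hold and the dilution occur together, since the first needs two single-agent deaths and the second few or none.

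The probabilities rest on assumed true rates and on reading the mark as strictly exceeded. Three in 20 would count if reaching exactly 6% were enough. Because the listed items may warrant a hold and the decision follows a safety review, the practical effect is on when that review is prompted.

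**What to change.** Amend section 8.5, with matching text in section 8.4:

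1. Reconcile the escalation counts, the 6% mark and the lead-in DLT rule so that no state satisfies one and fails another without a new event.
2. State the hand-over at 30 escalation patients and at the opening of expansion. This should cover what happens if the mark is already exceeded, and whether exactly 6% counts as passing it.
3. Count related deaths in combination-treated patients on their own denominator, from the first lead-in patient through all planned combination patients (up to 84), in addition to the trial-wide percentage.
4. Have the sponsor choose the limits and show the operating characteristics of the complete set of rules over a range of true rates and single-agent histories.

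The change is protocol wording plus a short calculation. Its downside is some additional false holds, of the order shown in the illustration above. The operating characteristics in item 4 would let the sponsor set that trade-off deliberately.

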8.6 Dose Modification Guidelines

8.6.1 Inpatient Dose Escalation

Patients who have tolerated treatment with modakafusp alfa well at the initially assigned dose may be allowed to increase their doses of modakafusp alfa in subsequent cycles of treatment following sponsor and investigator review of the available data. Inpatient dose escalation will be permitted only after all patients in the next higher dose level cohort have completed assessments for Cycle 1 and a decision has been made that this dose level does not exceed the MTD.

8.6.2 Criteria for Beginning or Delaying a Subsequent Treatment Cycle

To begin a new cycle of treatment with either modakafusp alfa alone or in combination with pembrolizumab, the patient must meet the following criteria:

- ANC must be $\geq 1000/\text{mm}^3$. Granulocyte-colony stimulating factor (G-CSF) can be used to reach this level.
- Platelet count must be $\geq 50,000/\text{mm}^3$ without transfusion support.

For therapy to resume, toxicity considered to be related to treatment with modakafusp alfa must have resolved to Grade ≤ 1 or baseline (Grade ≤ 2 for platelets and neutrophils), or to a level considered acceptable by the physician. If the patient does not meet the above-cited criteria for retreatment, initiation of the next cycle of treatment should be delayed for 1 week. At the end of that week, the patient should be re-evaluated to determine whether the criteria for retreatment criteria have been met.

If a subsequent cycle is delayed more than 14 days because of a related AE, the patient may be withdrawn from treatment unless there is clinical benefit as assessed by the investigator, with agreement by the sponsor's medical monitor. Modakafusp alfa dosing may be continued at the previously established safe dose level or below.

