8.2 Definitions of Dose-Limiting Toxicities

Toxicity will be evaluated according to the NCI CTCAE v 5. A DLT is defined as any of the following AEs that occur in the escalation phase or in the combination safety lead-in phase during Cycle 1 unless they are considered by the investigator to be clearly unrelated to therapy with modakafusp alfa.

- Any Grade 5 TEAE.
- Febrile neutropenia: Grade ≥ 3 neutropenia ($ANC < 1.0 \times 10^9/L$) with fever and/or infection, where fever is defined as a single temperature $> 38.3^\circ C$ or sustained temperature of $\geq 38^\circ C$ for more than 1 hour.
- Grade 4 neutropenia lasting > 7 days.
- Grade 4 thrombocytopenia lasting more than 7 consecutive days, or if platelet transfusion is required, or if Grade ≥ 2 bleeding happens at any moment. A platelet count $< 10 \times 10^9/L$ at any time is a DLT.

- Grade ≥ 3 thrombocytopenia lasting longer than 14 days or accompanied by Grade ≥ 2 bleeding.
- **Any Grade 3 immune-related AEs such as pericarditis, pneumonitis, cardiotoxicity, hepatitis, or neurotoxicity.**
- Delay in the initiation of Cycle 2 by more than 14 days from the calculated start date due to a lack of adequate recovery of treatment-related hematological or nonhematologic toxicities.
- Any Grade ≥ 3 nonhematologic toxicity **with the following exceptions:**
 - Grade 3 arthralgia/myalgia that responds to nonsteroidal anti-inflammatory drugs (NSAIDs) within 1 week.
 - Grade 3 fatigue that lasts < 3 days.
 - Grade 3 endocrine disorder that is managed with or without therapy and the patient is asymptomatic.
 - Grade 3 or 4 inflammatory reaction attributed to a local antitumor response.
 - Grade 3 or 4 asymptomatic laboratory changes (other than renal and hepatic laboratory values) that can be successfully corrected (reversion of Grade 4 events to Grade ≤ 2 , reversion of Grade 3 events to Grade ≤ 1 or baseline) within 72 hours.
 - Isolated Grade 3 elevation of ALT and/or AST that resolves to Grade ≤ 1 or baseline within 7 days.
 - Grade 3 nausea and/or emesis that can be controlled to Grade < 3 in ≤ 3 days with the use of optimal antiemetics (defined as an antiemetic regimen that employs both a 5-hydroxytryptamine 3 serotonin receptor antagonist and a corticosteroid given in standard doses and according to standard schedules).
 - Grade 3 rash and pruritis that respond to a standard treatment and resolve or improve to Grade < 3 within 7 days.

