8.6.3.1 Modakafusp Alfa Dose Modification Guidelines

[Table 8.b](#) provides general dose modification recommendations for modakafusp alfa. When the dose of modakafusp alfa is withheld on the basis of these criteria, clinical and laboratory re-evaluation should be repeated at least weekly or more frequently, depending on the nature of the toxicity observed, until the toxicity resolves to Grade ≤ 1 or baseline. If there are transient laboratory abnormalities that, based on investigator assessment, are not clinically significant, continuation of therapy without dose modification is permissible upon discussion with the sponsor. See details for managing specific AEs in [Section 8.10](#).

Table 8.b Dose Modification Recommendations for Toxicities Possibly Related to Modakafusp Alfa

Criteria	Action
Grade 1 AEs	No dose reductions or interruptions.
Grade 2 AEs	Patients experiencing Grade 2 AEs considered related to study treatment that are not easily managed or corrected and are not tolerable to the patient, or AEs that are not acceptable in the investigator's judgment, should have study treatment interrupted until the AE resolves to Grade ≤ 1 or baseline and then restarted at the same dose or, depending on the toxicity, at the previous safe dose level or below.
Grade 3, Grade 4 (not life-threatening per seriousness criteria), and Grade 4 asymptomatic laboratory AEs	Hold modakafusp alfa until resolution to Grade ≤ 1 or baseline, and then resume treatment at a reduced dose level. In case of Grade 3 hematological toxicity (anemia, thrombocytopenia, neutropenia, or lymphopenia) or Grade 3 asymptomatic laboratory AEs, the patient can continue at the same dose or a reduced dose at the investigator's discretion.
Grade 4 (life-threatening per seriousness criteria) AEs	Permanently withdraw the patient from the study.
AEs of all grades	If treatment has been held for >14 consecutive days without resolution of the toxicity (to baseline or Grade ≤ 1), consider permanently discontinuing study treatment unless there is clinical benefit for the patient as assessed by the investigator and with sponsor's approval. Treatment can be resumed at a reduced dose level after resolution of AEs to Grade ≤ 1 or baseline.

AE: adverse event.

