Treatment decisions will be based on a patient's platelet counts assessed before any transfusion. Low platelet counts (Grade 4) should cause scheduled infusions to be postponed or to be permanently discontinued. If at any time the platelet count is less than $10 \times 10^9/L$, or if the patient shows a bleeding tendency considered to be due to thrombocytopenia occurring after initiation of modakafusp alfa treatment, the patient should be withdrawn from modakafusp alfa treatment unless clinical benefit is observed and the investigator considers that thrombocytopenia can be managed with dose modifications. The investigator can consider the usage of corticosteroids, IVIG or thrombopoietin agonists in selected cases depending on severity, duration, transfusion requirements, and additional risk factors for bleeding and based on the suspected underlying mechanism. Platelet transfusion and close monitoring of platelet counts should follow institutional guidelines.

8.10.3 **Management of Immune-Mediated Adverse Events**

Pembrolizumab can cause pneumonitis, colitis, hepatitis, endocrinopathies, nephritis, skin adverse reactions, IRRs, and other immune-mediated AEs. Monitoring of these AEs is required in both the safety lead-in and expansion cohorts in the combination arm. Patients with AEs that are suspected to be related to pembrolizumab should be evaluated by appropriate methods, including physical examinations, laboratory tests, and imaging. These irAEs will be treated based on standard of care, local institutional guidance, the WARNINGS AND PRECAUTIONS section of the package insert, and the proper use guidance of pembrolizumab. It is recommended that the management of irAEs follow NCCN ([NCCN 2021](#)) or SITC ([Puzanov et al. 2017](#)) guidance.

8.11 **Blinding and Unblinding**

This is an open-label study.

8.12 **Description of Investigational Agents**

Modakafusp alfa is a humanized anti-CD38, IgG4, mAb fused to an attenuated IFN- α 2b. The initial frozen liquid modakafusp alfa formulation is used for all phase 1b dose escalation patients. The redeveloped lyophilized modakafusp alfa formulation is to be used in dosing phase 2 patients. Additional details can be found in the modakafusp alfa IB.

Pembrolizumab solution for infusion consists of 100 mg/4 mL (25 mg/mL) in a single-dose vial or powder for solution for infusion 50 mg (1 vial contains 50 mg pembrolizumab). Please refer to the pharmacy manual and the most recent pembrolizumab SmPC for details.

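### Protocol 8.6.2 and Table 8.b conflict on re-dosing after low platelets or neutrophils, so in a limited group of patients the Cycle 2 delay DLT depends on which one a site follows

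*Protocol*

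**What the plan says.** References are to the Protocol unless stated.

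- **8.6.2, counts.** To begin a cycle, ANC must be at least 1000/mm³ ("Granulocyte-colony stimulating factor (G-CSF) can be used to reach this level"), and "Platelet count must be $\geq 50,000/\text{mm}^3$ without transfusion support".
- **8.6.2, resolution of related toxicity.** Grade ≤1 or baseline is required, relaxed to Grade ≤2 "for platelets and neutrophils), or to a level considered acceptable by the physician".
- **8.6.3.1, Table 8.b.** For Grade 3, Grade 4 that is not life-threatening, and asymptomatic laboratory Grade 4: "Hold modakafusp alfa until resolution to Grade ≤ 1 or baseline", then resume at a reduced level. The same cell adds an exception: "In case of Grade 3 hematological toxicity (anemia, thrombocytopenia, neutropenia, or lymphopenia") or Grade 3 asymptomatic laboratory events, "the patient can continue at the same dose or a reduced dose", at the investigator's discretion.
- **8.10.2.** "Low platelet counts (Grade 4) should cause scheduled infusions to be postponed or to be permanently discontinued". The section gives no neutrophil level and does not say how it relates to 8.6.2.
- **8.2.** A DLT includes "Delay in the initiation of Cycle 2 by more than 14 days from the calculated start date due to a lack of adequate recovery" from treatment-related toxicity. No level is given and no section is cited.

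The number of patients with DLTs is a primary endpoint for phase 1b and the safety lead-in (5.2.1; SAP 5.1).

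**The concern.** After a low count, 8.6.2 and Table 8.b answer the same question differently. Table 8.b is stricter than 8.6.2 when counts have recovered to Grade 2. It appears looser when counts are still at Grade 3. Section 8.2 puts Grade ≥3 neutropenia at ANC <1.0 × 10⁹/L, which is below the ANC that 8.6.2 says must be met.

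The length of a Cycle 2 delay follows from whichever rule the site applies, and a delay of more than 14 days is a DLT. Part of the DLT count can then reflect site practice and not toxicity. The count drives the 3-patient decisions in 8.3 (first cohort) and 8.4 (lead-in) and is the input to the Bayesian logistic regression model (BLRM). A second primary endpoint, TEAEs leading to dose modification, is also touched, because SAP 7.12.1 counts a delay as a modification.

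**Working it through.** The plan states no figure for this point, so there is none to reproduce. The check applies each rule to the same counts.

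**Inputs.** The cycle is 21 days (Study Summary), so Cycle 2 Day 1 is due on Day 22. A delay of more than 14 days means dosing after Day 22 + 14 = Day 36. Entry platelets are ≥75 × 10⁹/L and entry ANC ≥1.0 × 10⁹/L (7.1). The only useful grade limit in the protocol is Grade ≥3 neutropenia at ANC <1.0 × 10⁹/L (8.2). Other limits are assumed: platelets Grade 1/2/3 down to 75/50/25 × 10⁹/L; ANC Grade 1 down to 1.5 and Grade 3 down to 0.5 × 10⁹/L.

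**Step 1: is 8.6.2 consistent with itself?** 1000/mm³ = 1.0 × 10⁹/L, so the ANC minimum is the same as Grade ≤2 by the protocol's own limit. For platelets, 50,000/mm³ = 50 × 10⁹/L is the same as Grade ≤2 under the assumed limits. The two statements agree; only the physician clause opens a gap.

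**Step 2: the rules side by side (× 10⁹/L).**

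| Count on Day 22 | Worst grade | 8.6.2 minimum | Table 8.b |
|---|---|---|---|
| Platelets 60 | 4 | met | hold |
| ANC 1.2 | 4 | met | hold, unless back to baseline |
| Platelets 40 | 3 | not met | can continue |
| ANC 0.8 | 3 | not met | can continue |

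For platelets the baseline alternative gives no relief, since entry already requires 75. For ANC it can, because entry allows 1.0.

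**Step 3: consequence for the DLT.**

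- *Patient A.* Platelets at Grade 4 for no more than 7 days, never below 10, Grade ≥3 for no more than 14 days in all, no bleeding or transfusion; 60 on Day 22, 75 on Day 38. Under 8.6.2: dosed Day 22, no DLT. Under Table 8.b: dosed Day 38, delay 38 − 22 = 16 days, a DLT, with no other DLT criterion met.
- *Patient B.* No fever or infection, no G-CSF; ANC 0.8 on Day 22 and 1.0 on Day 38. Under the 8.6.2 count: 16-day delay, DLT. If the Table 8.b discretion or the physician clause is read to permit infusion: dosed Day 22, no DLT.
- *Patient C.* Platelets 40 from Day 15 to Day 37, 50 on Day 38. Held under 8.6.2, this is a DLT by delay and also by the separate criterion of Grade ≥3 thrombocytopenia beyond 14 days, so the delay criterion is not decisive. If infusion were given on Day 22 under the Table 8.b discretion, the escalation DLT window would close after 22 − 15 = 7 days at Grade 3.

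**Step 4: effect on a cohort of 3.** In the lead-in, 0/3 means the regimen could be selected, 1/3 adds 3 patients, and ≥2/3 moves to the next lower dose level (8.4). Let q be the share of patients whose status depends on the rule followed. The documents do not give q, so a range is assumed. P(at least 1 of 3) = 1 − (1 − q)³:

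| q | 2% | 5% | 10% | 20% |
|---|---|---|---|---|
| P | 5.9% | 14.3% | 27.1% | 48.8% |

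With an assumed 10% DLT rate from other causes, P(0/3) = 0.9³ = 72.9%. If all patients in the gap are counted as DLTs, the rate is 0.10 + 0.90q and P(0/3) = (0.90 − 0.90q)³:

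- q = 5%: 0.855³ = 62.5%
- q = 10%: 0.81³ = 53.1%
- q = 20%: 0.72³ = 37.3%

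**The case against.** Much of the text can be read together. Table 8.b is titled as recommendations and described as general, while 8.6.2 says what the patient must meet. Permission to continue after Grade 3 can be read as a choice of dose level, with 8.6.2 still deciding when the infusion is given. The physician clause sits in the sentence on resolution of toxicity and need not override the numeric counts. These readings are fair, and they weaken Patient B. They do not remove Patient A: Grade ≤1 and Grade ≤2 are different recovery levels for the same patient, and 8.6.3.1 also asks for re-evaluation until Grade ≤1 or baseline.

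Several stronger inferences are tempting and are not supported.

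- A reader might infer that four places give four different levels for both counts. Three sections bear on re-dosing (8.6.2, Table 8.b, 8.10.2), only the first two cover neutrophils, and the two statements within 8.6.2 agree.
- A reader might infer that 8.10.2 exempts Grade 3 platelets from postponement. It names Grade 4 as a trigger and does not say it is the only one, so it can be followed together with 8.6.2.
- A reader might infer that the situation is common from 5 of 17 patients (29.4%) with thrombocytopenia and 3 of 17 (17.6%) with neutropenia in 4.3.3. Grade ≥3 is stated only for the 3 neutropenia cases, and neither figure counts Cycle 2 delays.

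The DLT effect is also contained. Section 8.2 separately captures Grade ≥3 thrombocytopenia beyond 14 days and Grade 4 neutropenia or thrombocytopenia beyond 7 days. G-CSF may be used to reach the ANC level, and the restriction in 8.8.3 covers only Cycle 1 of escalation, unless medically indicated. Later events can still inform the recommended dose (8.2) and be fed to the BLRM (Appendix E), and dose decisions use all emerging data (8.3).

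**Conclusion.** Wrong as written; should be fixed. Section 8.6.2 and Table 8.b set different recovery levels for one decision, Table 8.b's Grade 3 discretion sits against the 8.6.2 minimum, and the delay DLT cites no rule. A limited group can be a DLT or not depending on the passage followed: mainly patients with Grade 2 counts after a brief Grade 4 nadir, or with slow afebrile neutropenia.

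The frequency is unknown, and the probabilities above are only as good as the assumed q and the assumed 10% background rate. What needs no assumption is that one reclassified patient moves a 3-patient lead-in from 0/3 to 1/3, or from 1/3 to 2/3. The Grade ≤1 against Grade ≤2 conflict does not depend on the assumed grade limits; those only place the example counts. The documents do not support going further and saying that the DLT endpoint as a whole is unreliable.

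**What to change.** - Reconcile 8.6.2, 8.6.3.1 with Table 8.b, and 8.10.2 so that one stated re-dosing criterion applies to platelets and one to neutrophils. The sponsor chooses the levels; this review takes no position on them.
- State whether the physician clause in 8.6.2 and the Grade 3 discretion in Table 8.b apply to the numeric counts in 8.6.2.
- In 8.2, define adequate recovery in the Cycle 2 delay criterion by cross-reference to the reconciled criterion.
- Leave the other 8.10.2 instructions in place, including withdrawal for platelets below 10 × 10⁹/L or bleeding. Replacing that section with a bare cross-reference could delete them.

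The cost is protocol wording in four sections, with no added visits, tests or patients.
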